1.2 Research Significance

HTN is the leading risk factor for death and disability-adjusted life years.² In addition to being a risk factor for stroke³ and renal dysfunction⁴, HTN is also the primary risk factor for heart disease, which is the leading cause of death in the US and kills close to 650,000 people per year.⁵ In the US, 33% of individuals have HTN⁶ and for adults with HTN, BP control decreased from 54% in 2013-2014 to 44% in 2017-2018.⁷ BP is elevated at 44% of all ED visits- compared to 27% of primary care doctor visits.⁸ Data demonstrates that ED patients' elevated BP is from HTN, and not a result of pain or anxiety from the ED visit.^{9,10} From 2006 to 2012, HTN-related ED visits made up 24% of all ED visits, and rose 5% per year.¹¹

ED patients may have no interaction with the healthcare system outside the ED, and thus be difficult to reach for interventions. There are 139 million ED visits annually in the US,¹² and ED visits for primary-care needs are highest for uninsured and low-income patients, suggesting a lack of access to primary care for these patients.¹³ EDs tend to serve in a safety net capacity for underserved patients.¹⁴ The proportion of adults with uncontrolled HTN is greater for those without a usual care facility than those with one,⁷ suggesting high rates for ED patients without a source of usual care. Controlled BP is also less likely for people with HTN and no insurance than those with private insurance.⁷

Compared to non-Hispanic whites, African Americans are 40% more likely to have high BP,¹⁵ are less likely to have it under control,^{7,15} are 20% more likely to die from heart disease,¹⁵ and are more likely to have heart failure at a young age (<50 yrs).¹⁶ Adults with limited English proficiency (LEP) are more likely to have poorly controlled HTN than adults with English proficiency,¹⁷ and the management of asymptomatic HTN in the ED can be complicated by language and cultural differences between the patient and the provider.¹⁸ Several studies have shown that a lack of HTN knowledge is a common barrier to HTN control,¹⁹⁻²¹ and providing information that is culturally-sensitive and relevant is especially important.^{21,22} Culturally relevant programs using community health workers (CHWs) have proven effective in controlling BP for people with HTN.^{23,24} CHWs can provide culturally appropriate health promotion and health education and assist in accessing medical services.²⁵

Youth can act in a CHW capacity for the adults with whom they live. A youth-led HTN education intervention can warrant benefits to both hypertensive adults and the youth themselves. For adults, a lack of HTN knowledge is a common barrier to HTN control,¹⁹⁻²¹ while social support is a strong facilitator^{19,21,26} especially for African Americans.²⁷ Youth have shown increased confidence when given the responsibility to provide health education and care navigation to others.²⁸⁻³⁰ Guided by the Social Cognitive Theory³¹ and findings from several studies, youth who contribute to health programs and services can also expand their own knowledge and increase their healthful decision making capacity.^{30,32,33,34}

1.3 Research Design and Methods

A. Research Procedures

Aim 1 (Group 1): This aim will develop the intervention through community feedback and user-centered design methods.

First, we will first create an outline of a prototype for a youth-led HTN education digital badge. A digital badge is a type of credential³⁵ that serves as a virtual resume of knowledge and competencies for stakeholders such as peers, schools, or potential employers.³⁶ The digital badge will have a playlist of 6 online experiences (XPs) on HTN information. Each XP will be self-guided with step-by-step instructions to learn material, complete a task, and submit evidence of completion (e.g. photographs). Information that contributes to the playlist XPs will come from reputable health sources, such as the Centers for Disease Control and Prevention³⁷ and American Heart Association,³⁸ and will include information on local federally qualified health centers to establish primary care. The digital badge at this stage will be a skeleton outline of possible content for inclusion in the eventual digital badge intervention.

Second, design sessions will be held (led by the PI for English sessions and a Spanish-speaking RA for Spanish sessions) with community members to get feedback on the digital badge prototype. These sessions will be in the format of focus groups or individual interviews. At the start of each session, participants will complete a brief questionnaire, then participants will be provided a menu of possible digital badge content areas and various possible content within each area to provide their input on which they would prefer to see be included in the digital badge. Participants will also discuss acceptability, feasibility, obstacles and solutions for digital badge implementation. Participants will be asked to comment in an open-ended style with prompts used to guide the discussion. Design sessions are expected to last about 1.5 hours and will be audio recorded. The digital badge intervention will then be refined to reflect the input of discussion session participants prior to being used in Aim 2.

Aim 1a: The hypertension knowledge assessment being used in the study has not been used before on youth or Spanish-speaking populations, so we are looking for participants from the design sessions to take part in one-on-one Zoom cognitive interview sessions about their feedback on the assessment. (Spanish documents will be added as a future modification prior to Aim 1a taking place with Spanish-speakers.)

1. Prior to the youth cognitive interviews, a health literacy expert will run the assessment through software for health literacy. Next, members of the study team, including experts in pediatrics and health literacy will look over the assessment. This group will meet to go through the wording of the instructions, items, and responses for appropriateness at the teenager level.
2. We will recruit a subset of interested youth from the design session participants (Aim 1) for the one-on-one youth cognitive interviews, which will take place over Zoom. The participant will complete a brief demographic survey and then complete the hypertension knowledge tool and will provide overall reactions and feedback. Then they will provide feedback on each question one at a time on wording, understandability, clarity, and relevance of instructions, items, and responses. Youth must sign an additional consent form (and parental permission form if under 18 years old) and will receive a \$10 gift card for their time.
3. The group from step #1 will meet again and discuss what should be changed in the assessment tool based on feedback from the youth. The refined assessment will then be used in Aim 2.
4. Spanish-speaking sessions will also take place implementing one-on-one cognitive sessions as explained in step #2 above. These sessions will not take place until Spanish documents are submitted for IRB approval in a future modification.

Aim 2 (Group 2): One cohort will be recruited out of the ED. This cohort implements a two-arm randomized controlled trial to test the effectiveness of the intervention.

1. A member of the study team (usually the research assistant (RA)) will determine initial eligibility by checking the patient's chart/ED board for their BP. The RA will ask patients with BP $\geq 130/80$ mmHg if they have a history of HTN. If yes, the RA will ask the patient: 1) If they have an existing relationship (such as family member) with a 14-24-year-old, and 2) If the youth has access to internet or a data plan, as well as a smart phone or computer (to complete the digital badge intervention).
2. If the patient is eligible and interested in participating in the study, the RA will discuss the study with the patient, answer questions, and obtain written consent.
3. The RA will then collect the patient's BP using the study BP cuff (which is then used for patient follow-up visits so that there is no variation in BP instrument measurements) and follows the BP measurement protocol. Adult completes baseline assessments including hypertension knowledge.
4. The RA will give the patient a study flyer to bring home to the potential youth participant and will collect the patient's contact information. The patient will be asked to share the information with the youth and call the study team if both adult and youth are interested in participating. If the adult is willing to provide the youth's contact information, we will collect it.
5. If the team does not hear from the patient after 3 days, they will contact (call, email, and/or text) the patient to follow-up about participation. If we have the youth's contact information from the adult, we will contact the youth directly and tell them that we received their information from the adult (see youth recruitment script). The adult patient and youth must both agree to participate in the study for the dyad to participate.
6. After a member of the study team discusses the study with the youth (and parent or legal guardian if youth is 14-17), answers questions, and obtains written consent (including parental/legal guardian consent if youth is 14-17 years old).
7. Youth completes baseline assessments including hypertension knowledge and self-efficacy scales.
8. Each dyad will be randomized into one of two arms- either intervention or control arm:

Arm 1- Intervention: Participants in the intervention arm will receive the youth-led HTN education digital badge to complete, which will be comprised of a 6-week playlist of one module per week comprising the playlist. Youth will learn from the module and will teach the adult in their dyad about hypertension education in each week's themed module.

Arm 2- Control: For dyads that are randomized into the control arm, the youth will complete job readiness digital badges. These will include a Career & Job Readiness digital badge playlist, with such playlists as, "Interview Preparation", "Resume Ready", and "Professionalism". While this group may complete multiple digital badges, the total time needed to complete the badges will be approximately equivalent to that of the intervention group (eg. one hour per week for each arm).
9. For both arms, youth must submit evidence of completion (eg. photograph, document) as specified in the playlist's instructions. Evidence will be reviewed by the study team and a digital badge is received if all XPs are satisfactorily completed. If not satisfactorily completed, then a note will be sent back to the youth on how to fix or improve the evidence and resubmit.

10. Adult participants in both arms return to RWJUH for follow-up BP check and complete follow-up assessments- blood pressure self-care scale, hypertension knowledge assessment, and self-efficacy to manage hypertension scale. They will receive an incentive for returning at 1 week and 2 months after completion of digital badge. Youth will complete follow-up assessments of hypertension knowledge and confidence in managing blood pressure of adults at the same timepoints but will be done remotely/electronically.

Due to challenges recruiting youth through adults in the ED, we will be adding a cohort to the study. For this new cohort of the study, we will recruit interested youth from NBHSTHS. Students will be asked to pair themselves with an adult (18+) (preference for adult who has been diagnosed with hypertension) with an existing relationship with the student where it would be feasible to complete an online module together 1 hour per week for 6 weeks. The adult must be fluent in English or Spanish and the student must be able to speak the fluent language of the adult. For this cohort, study procedures are as follows:

1. We will recruit students at NBHSTHS for information sessions (see youth recruitment flyer).
2. We will hold information sessions at the school about the study.
3. After info session, student decides if they want to participate and determines if an adult in their life also wants to participate. Student will give their adult a recruitment flyer and will then complete a Redcap form with their info and adult's info including best time to reach adult to complete consent form and parent info for parental permission (if adult is not parent) on Zoom (could also complete at school if needed).
4. Student consent, adult consent, and parental permission forms will be obtained using e-consent in Redcap.
5. Students will be grouped into a training session at school. At the start of the session, students will complete study assessments including demographics and hypertension knowledge in Redcap. (Adults will also complete their pre-intervention assessments remotely this week via Redcap.)
6. The following week, the student group will have a second in-school session to evaluate their knowledge on to implement the intervention on their adult at home by implementing it on a "practice adult" (one of the research assistants) who will have a checklist where they check off that the student is able to complete the intervention correctly and teach them anything that they have questions about or do not do correctly. Youth completes a HTN knowledge assessment at the end of this session.
7. For the following 6 weeks, students will implement the digital hypertension education intervention with their adult at home- completing one module per week (each module will take about one hour). (Participants will complete feedback assessments at the end of each module.)
8. At the end of the 6 weeks, adult and youth participants will again complete the assessments that they completed before the 6-week intervention (with the exception of demographics).
9. Halfway through the 6-week intervention and at the end of the intervention, any participants (youth or adult) who is interested (not required) can complete interviews about feedback on the intervention (on Zoom or in person).

10. 4 weeks after the end of the 6-week intervention, adult and youth participants will complete the assessments a final time.

Aim 3 (Group 2):

Questionnaire: At the conclusion of each hypertension education module in the intervention, all participants in the intervention group will be asked to complete a questionnaire on the intervention's acceptability and feasibility as part of the requirement for module completion. Participants must complete the questionnaires to receive their study incentive.

Interviews: We will also conduct one-on-one phone interviews with interested participants from the intervention group for more in-depth information on intervention acceptability, feasibility, and fidelity. These will take place halfway through the intervention and at the end of the intervention. Interviews will be available in English and Spanish, and be audio recorded.

B. Data Points

Aim 1 (Group 1): Participation will be a one-time design session that will take place prior to the start of the RCT.

Aim 1a: Participation will be a one-time cognitive interview session.

Aim 2 (Group 2): For the first cohort, BP will be collected at baseline in the ED and at 1 week and 2-month post-intervention follow-ups at RWJUH. Pre- and post-intervention change in HTN knowledge, adult BP self-care, adult self-efficacy to manage HTN and youth confidence in managing adult BP will be collected during the same timepoints.

For the school cohort, youth and adult participants will complete study assessments after consent is signed. Fidelity of the intervention will be collected on youth the following week, and youth will complete a HTN knowledge assessment at the end of this session. At the end of each of the 6 intervention modules, participants will complete module feedback assessments. At the end of the 6 week intervention and then 1 month after the end of the 6 week intervention, all participants will complete study assessments.

Aim 3 (Group 2): Implementation data points will be collected at the end of each module (surveys) and at the midpoint and end of the intervention period (6 weeks post-baseline) (interviews).

C. Study Duration

Aim 1 (Group 1): Participation will be a one-time design session that will last approximately 1.5 hours.

The duration of this aim is expected to be about 3 months.

Aim 1a: Participation will be a one-time cognitive interview session that will last approximately 30 minutes. The duration of this aim is expected to be about 3 months.

Aim 2 (Group 2): For the first cohort, participation duration will be 3.5 months (6 weeks for digital badge intervention plus 2 months for final follow-up after completion of intervention). Baseline data collection is expected to take approximately 20 minutes. During the 6-week digital badge intervention, participants will spend approximately 1 hour per week on the digital badge. Follow-up data collection is expected to take approximately 20 minutes per session (with sessions at 1 week and 2 months).

For the school cohort, youth participation duration will be 12 weeks (about 3 months) (2 weeks for training, 6 weeks for digital badge intervention plus 4 weeks for final follow-up after completion of intervention). Two training sessions at weeks 1 and 2 are expected to take about 40-60 minutes each. Baseline data collection is expected to take approximately 20 minutes. During the 6-week digital education module, participants will spend approximately 1 hour per week on the module. Follow-up data collection is expected to take approximately 20 minutes per session (with sessions at 8 week and 12 weeks).

Adult participation duration will be 10 weeks (6 weeks for digital badge intervention plus 4 weeks for final follow-up after completion of intervention). Baseline data collection is expected to take approximately 20 minutes. During the 6-week digital education module, participants will spend approximately 1 hour per week on the module. Follow-up data collection is expected to take approximately 20 minutes per session (with sessions at the end of the intervention and 1 month later).

Aim 3 (Group 2): The quantitative implementation data questionnaire is expected to take approximately 5-10 minutes to complete. The qualitative interviews will last approximately 30-45 minutes each.

The duration of Aims 2 and 3 are expected to be 1.5 years total for the study.

D. Endpoints

Aim 1: Participation will be a one-time design session that will last approximately 1.5 hours.

Aim 1a: Participation will be a one-time cognitive interview session that will last approximately 30 minutes.

Aims 2 and 3: For the first cohort, participation ends 2 months after the end of the 6-week intervention (3.5 months after baseline). For the school cohort, participation ends after 12 weeks for youth and after 10 weeks for adults.

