 - b. 4-item Feasibility of Intervention Measure (FIM) scale¹ to measure intervention feasibility by participants
 - c. Amount of time spent for hypertension education module completion
 - d. Feedback on the hypertension education module.

[figure not shown]
2. Data pulled from the digital badge platform will measure intervention fidelity. This information will include:
 - a. Measures of adherence to program protocol: 1) # of participants who completed the entire digital badge, 2) Number of days between each XP (as XPs are meant to be administered weekly), 3) # pieces of submitted evidence rejected by the program reviewer for each XP
 - b. Measures of dose of intervention delivered: 1) Number of XPs completed in the playlist, 2) Which XPs were completed by participants who did not complete the entire digital badge

- **Qualitative:** Phone/Zoom interview participants will describe obstacles and successes that they encountered with the digital badge. We will also ask participants about acceptability and feasibility of the digital badge, including asking them to explain reasoning behind their favorite and least favorite module and most and least informative module.
- **Ethnographic Studies, Interviews, Or Observation:**
Aim 1: Design sessions will explore the acceptability and feasibility of the prototyped digital badge and web-based implementation process, including potential obstacles and solutions.
Aim 1a: We will recruit a subset of interested youth from the design session participants (Aim 1) for the one-on-one youth cognitive interviews, which will take place over Zoom. The participant will complete a brief demographic survey and then complete the hypertension knowledge tool and will provide overall reactions and feedback. Then they will provide feedback on each question one at a time on wording, understandability, clarity, and relevance of instructions, items, and responses.
Aim 2: Not applicable.
Aim 3: Phone/Zoom interview participants will describe obstacles and successes that they encountered with the digital badge. We will also ask participants about acceptability and feasibility of the digital badge, including asking them to explain reasoning behind their favorite and least favorite modules and most and least informative modules.
- **Subject Identifiers:**

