4.6 Economic Burden and/or Compensation for Subjects

A. Expenses

Participants will incur no expenses for study participation.

B. Compensation/Incentives

Aim 1: Participants will receive a \$20 gift card.

Aim 1a: Participants will receive a \$10 gift card.

Aim 2: In the first cohort, youth in both arms will receive a \$20 gift card after completing baseline assessments, a \$20 gift card after completing the first 3 weekly modules (halfway

through the intervention), a \$20 gift card after completing all 6 weekly modules (end of intervention) and questionnaires one week later, and a \$10 gift card after completing questionnaires two months after the end of the intervention.

Adults in both arms will receive a \$20 gift card after completing baseline assessments and a \$40 gift card at each follow-up visit for BP check (1 week and 2-months). Adults will also receive transportation vouchers (for either parking or public transit) for follow-up visits.

In the school cohort, adults and youth will receive \$80 in gift cards total if they complete the study. Youth will receive: a \$20 gift card after completing the second in-school session, a \$20 gift card after completing the first 3 weekly modules (halfway through the intervention), a \$20 gift card after completing all 6 weekly modules (end of intervention) and questionnaires, and a \$20 gift card after completing questionnaires 1 month after the end of the intervention. Adults will receive: a \$20 gift card after completing the second in-school session, a \$20 gift card after completing the first 3 weekly modules (halfway through the intervention), a \$20 gift card after completing all 6 weekly modules (end of intervention) and questionnaires, and a \$20 gift card after completing questionnaires 1 month after the end of the intervention. **Aim 3:** Interview participants will receive a \$10 gift card per interview for their time.

C. Compensation Documentation

To document compensation, we will keep a master list of date, subject name, amount and type of compensation received.

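### The ED cohort's follow-up BP visits are anchored sometimes to badge completion and sometimes to a calendar date; one anchor is needed for every randomised dyad

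*Combined protocol and SAP*

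**What the plan says.** Several sections describe when the ED cohort's adults come back for BP, and they use two kinds of anchor.

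**Counted from completion.**
- Section 1.3 A, Aim 2 step 10: "Adult participants in both arms return to RWJUH for follow-up BP check", and then "They will receive an incentive for returning at 1 week and 2 months after completion of digital badge".
- Section 1.3 C gives the length of participation as "6 weeks for digital badge intervention plus 2 months for final follow-up after completion of intervention".
- Section 4.6 B pays youth "after completing all 6 weekly modules (end of intervention) and questionnaires one week later", which equates finishing the modules with the end of the intervention.

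**Counted by the calendar.**
- Section 1.3 D: "participation ends 2 months after the end of the 6-week intervention (3.5 months after baseline".
- For Aim 3, sections 1.3 B and 1.9 A (Timing and Frequency) place the end of the intervention period six weeks after baseline.

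**Neutral or loose.** For BP itself, 1.3 B and 1.9 A say only that the visits are 1 week and 2 months post-intervention. Section 1.6 B, taken word for word, counts 1 week and 2 months from baseline.

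**Completion can move or fail.** Under step 9, if submitted evidence is unsatisfactory, "then a note will be sent back to the youth on how to fix or improve the evidence and resubmit". Section 1.9 A plans to record "Number of days between each XP (as XPs are meant to be administered weekly" and which experiences were done by those who did not finish. Hypothesis 3 expects only that most will finish. Control youth may complete more than one badge.

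Section 6.1 compares mean BP change from baseline to the 2-month follow-up by arm.

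**The concern.** The 2-month BP reading is the primary outcome. Comparing the arms on it is like for like only if that visit means the same elapsed time for every dyad. If badge completion starts the clock, elapsed time depends on how quickly the youth works, on whether evidence is sent back, and on whether the badge is finished at all. All of these happen after randomisation, and the two arms do different badges.

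Three things follow from using step 10 as the visit schedule:
- Slow dyads are measured later than fast ones.
- A dyad that never finishes has no date for its primary reading, so it is at risk of dropping out of the comparison for a reason linked to engagement.
- In the control arm, where several badges may be done, it is unclear which completion counts.

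**Working it through.** **Inputs from the documents.** Planned intervention: 6 weeks = 42 days. Visits: 1 week and 2 months afterwards. Stated participation: 3.5 months after baseline (1.3 C and D). I take a month as 30.44 days, so 2 months = 60.88, about 61 days.

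**The plan's own figure.** 42/30.44 + 2 = 1.38 + 2 = 3.38 months; with 4-week months, 42/28 + 2 = 3.50. The stated 3.5 months therefore reproduces as a rounded figure, provided the intervention starts on the day of the ED baseline.

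**Timing under each anchor.** Let g be the days from ED baseline to the start of the intervention and d the days taken to finish the badge. The documents give neither, so every value below is an assumption.
- Anchored to completion: visits on day g + d + 7 and day g + d + 61.
- Anchored to a fixed 6-week period from the start: day g + 42 + 7 and day g + 42 + 61.
- Difference for either visit: d − 42 days.

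With g = 0, the fixed dates are day 49 and day 103. The completion-based dates are:

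| d (days) | 1-week visit | 2-month visit | Shift from fixed dates |
|---|---|---|---|
| 28 | 35 | 89 | −14 |
| 35 | 42 | 96 | −7 |
| 42 | 49 | 103 | 0 |
| 49 | 56 | 110 | +7 |
| 56 | 63 | 117 | +14 |
| 84 | 91 | 145 | +42 |
| never finished | no date | no date | undefined |

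**The gap before the start.** In 1.3 A the baseline BP is taken in the ED. Contact with the youth, consent and randomisation come afterwards, and the team waits 3 days before chasing a reply. So g is normally above zero. With g = 14 and d = 42, the final visit falls on day 14 + 42 + 61 = 117, which is 14 days after day 103 although the badge took exactly 6 weeks. With g = 28 it is day 131, or 28 days after. Finishing in 6 weeks therefore reconciles badge completion with the end of a 6-week intervention. It reconciles either with a date counted from baseline only if g is close to zero.

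**What cannot be computed.** The documents give no completion rate, no BP standard deviation and no time trend in BP. The day shifts cannot be turned into mm Hg.

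**The case against.** The strongest reply is that the sections can be read together. Section 1.3 C counts from completion, as step 10 does, and 4.6 B equates finishing the modules with the end of intervention. With 6 weeks as the planned length, 1.3 D merely states the expected total, in a paragraph about how long participation lasts. The Aim 3 wording, six weeks after baseline, could even support treating step 10 as shorthand for the end of the 6 weeks. That reply stands: a reader might infer a flat contradiction between step 10 and 1.3 C–D, and the documents do not support one. What it does not do is settle which sense governs the BP visits, because the calendar wording is written for Aim 3 and the completion wording for the visits themselves.

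A second reply is that the quoted sentence concerns payment. It does, but it is the only ED-cohort procedure step that times the adult returns, and it ties visit and payment to the same event.

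A reader might also infer that only completers are followed up or paid. The documents do not say so. Step 10 has adults in both arms returning, and 4.6 B pays adults a "gift card at each follow-up visit for BP check (1 week and 2-months".

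Finally, section 1.10 is headed as the timetable for this very cohort and its content is not shown. It may hold dates, windows or a rule for non-completers, so no claim is made that these are absent.

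The choice of anchor is partly a design preference. Aim 2 places the outcome at 2 months post-intervention, and a calendar anchor measures slow dyads sooner than 2 months after their last module.

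**Conclusion.** The point holds as an inconsistent anchor for the primary outcome visit, worth fixing before follow-up data accrue. Used as the visit schedule, step 10 moves both BP visits by d − 42 days and leaves a dyad that never finishes without a date. Resubmission, the recording of days between experiences and the expectation of some non-completers show that the plan itself foresees departures from 6 weeks.

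A reader might go further and infer that the arm comparison is biased. The documents do not support that: neither size nor direction can be derived, control badges are meant to take about the same total time as the intervention, and no difference in completion between arms is predicted here.

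The conclusion rests on taking step 10 literally and on section 1.10 not already fixing the dates. The values of d and g are illustrative. No sample size, power or alpha figure is affected.

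**What to change.** In step 10 of 1.3 A, and consistently in 1.3 C–D, 1.6 B and 4.6 B, define one calendar anchor for every randomised dyad in both arms. One example is the end of a 6-week period counted from randomisation, which gives visits at about day 49 and day 103 after randomisation. A start date set the same way in both arms would also serve. State that adults are invited, measured and paid at those visits whether or not the badge is completed. In 1.6 B, replace the loose counting from baseline with the same definition. If the section 1.10 timetable already fixes these dates, align the other sections with it.

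The cost is a few sentences and a few more gift cards. The drawback is that some slow dyads will be measured less than 2 months after their last module, and some visits may come before it.
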